3.2 Randomisation

The patient number will be an 8 digits code: 3 digits country code (the study is only conducted in the US, US Country Code is 840), 2 digits site number and 3 digits patient number. Each participating investigative study centre will be assigned a 2 digit investigative study centre number (eg, 01, 02, 03, and up) on enrolment.

Each subject will receive a 3 digit Screening number in sequential order at the Screening Visit after the consent form is signed (eg, 001, 002, 003), regardless of the investigative study centre at which the subject is enrolled.

Enrolled subjects who fail Screening or discontinue study participation early, regardless of whether treatment was received or not, will retain their Screening number and a new number will be assigned to the next enrolled subject.

For subjects who remain eligible after the Screening Placebo Run-In period, randomization numbers (which are separate from the screening numbers) will be assigned by the Interactive Response Randomization System, which is integrated into the Electronic Data Capture (EDC) system. Details of assignment of subject numbers will be provided as a separate document.

Subjects will be randomly assigned to receive litoxetine or matched placebo BID in a 2:1 ratio.

4. Analysis Sets

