Categorical variables will be summarised by using frequency distributions and percentages.

For all analyses, hypothesis testing will be carried out at the alpha = 0.05 level (two-sided) when comparing treatments. P-values will be rounded to three decimal places. Statistical significance will be declared if the rounded p-value will be less than or equal to 0.05.

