$$\Delta = \exp\left(\log\left(\frac{\%UIE_{Litoxetine}}{\%UIE_{Placebo}}\right)\right) = \frac{\%UIE_{Litoxetine}}{\%UIE_{Placebo}}$$

$\%UIE_i$ is the ratio of the total number of urinary incontinence episodes in a week at endpoint (Visit 6) ($UIE_{i,end}$) to the total number of urinary incontinence episodes in a week at baseline ($UIE_{i,base}$) for arm i , with i equal to Litoxetine or Placebo.

An ANCOVA will be performed to compare δ to 0; the test will provide an appropriate p-value with a significance level alpha equal to 0.05. This p-value will be computing the probability of observing a difference among arms.

Numbers of incontinence episodes equal to 0 (not missing) will be imputed as 0.4 to allow for the log transformation.

2. Absolute change from end of the Screening Placebo Run-In Period to Week 8 in the number of incontinence episodes/24 hours (daily average)

The analysis planned is an analysis of covariance model (ANCOVA). Absolute change in the total number of incontinence episodes/24 hours is the response variable. The factor variables will be dose and centre. The covariate will be end of the Screening Placebo Run-In Period episodes of incontinence.

Number of incontinence episodes/24 hours will be computed as Total Number of incontinence episodes recorded during the 7-day period and entered in the eCRF divided by 7, as defined in Section 5.4.

The hypothesis test being conducted is as follows:

$$H_0: \Delta UIE_{Litoxetine} - \Delta UIE_{Placebo} = 0$$
$$H_1: \Delta UIE_{Litoxetine} - \Delta UIE_{Placebo} \neq 0$$

Where ΔUIE_i is the absolute change, for subjects in arm i , in the number of incontinence episodes/24 hours as defined above from baseline ($UIE_{i,base}$) to the final measurement ($UIE_{i,end}$):

$$\Delta UIE_i = UIE_{i,end} - UIE_{i,base}.$$

Where i goes from 1 to 2 and it represents the 2 arms: Litoxetine and Placebo.

3. Proportion of subjects who become continent at Week 8

A subject is defined as continent if s/he has no incontinence episodes at Visit 6 (Week 8). Frequencies will be used to describe the proportion of subjects who are continent at Week 8. The proportion will be computed on the total number of subjects for each arm at baseline. The category Missing will be included in the analysis, to consider subjects who do not attend the visit or who have missing values for that visit.

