Differences between groups will be evaluated using Chi-square test or Fisher's exact test (if more than 20% of the cells in a contingency table have counts less than 5).

4. Change from end of the Screening Placebo Run-In Period to Week 8 in the number of incontinence pads used per week

The analysis planned is an analysis of covariance model (ANCOVA). Absolute change in the number of incontinence pads used per week is the response variable. The factor variables will be dose and centre. The covariate will be the number of pads used at the end of the Screening Placebo Run-In Period.

Number of incontinence pads used per week will be derived for the eCRF, as defined in Section 5.4.

The hypothesis test being conducted is as follows:

$$\begin{aligned} H_0: \Delta \text{Pads}_{\text{Litoxetin}} - \Delta \text{Pads}_{\text{Placebo}} &= 0 \\ H_1: \Delta \text{Pads}_{\text{Litoxetin}} - \Delta \text{Pads}_{\text{Placebo}} &\neq 0 \end{aligned}$$

Where ΔPads_i is the absolute change, for subjects in arm i , in the number of incontinence pads used per week from baseline ($\text{Pads}_{i,\text{base}}$) to the final measurement ($\text{Pads}_{i,\text{end}}$):

$$\Delta \text{Pads}_i = \text{Pads}_{i,\text{end}} - \text{Pads}_{i,\text{base}}.$$

Where i goes from 1 to 2 and it represents the 2 arms: Litoxetin and Placebo.

5. Percentage change from end of the Screening Placebo Run-In Period to Week 8 in the number of nocturia episodes in a week

The analysis planned is an analysis of covariance model (ANCOVA). Percentage change in the total number of nocturia episodes in a week is the response variable. The factor variables will be dose and centre. The covariate will be end of the Screening Placebo Run-In Period episodes of incontinence.

The number of nocturia episodes in a week is the total number of nocturia episodes recorded over the 7-day period and entered in the eCRF, as defined in Section 5.4.

The analysis will be carried out as described in section 6.9 point 1.

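### On its plain reading, the ITT continence test treats Missing as an outcome category, so unequal dropout alone can make it significant

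*SAP*

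**What the plan says.** Continence at Week 8 is the third of five secondary efficacy endpoints (SAP 2.4). SAP 6.9 point 3 treats a subject with no episodes at Visit 6 as continent and fixes the denominator: "The proportion will be computed on the total number of subjects for each arm at baseline". It then adds: "The category Missing will be included in the analysis, to consider subjects who do not attend the visit". Attendees without a Visit 6 value fall in the same category. The next paragraph gives the test: "Differences between groups will be evaluated using Chi-square test". Fisher's exact test takes its place when over a fifth of the table's cells hold fewer than 5 subjects. SAP 6.3 sets the decision rule: "hypothesis testing will be carried out at the alpha = 0.05 level (two-sided) when comparing treatments". The threshold applies after rounding: "Statistical significance will be declared if the rounded p-value will be less than or equal to 0.05".

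Three other places bear on the point:

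- SAP 6.9 runs efficacy on the ITT and PP populations. SAP 4.1 admits a subject to PP only with a valid Visit 6 value.
- SAP 6.1 multiply imputes missing Visit 6 episode counts in the ITT population, and 6.3 uses observed and imputed counts for the ITT analysis of episodes. Neither says whether continence, which derives from the same count, is covered.
- SAP 3.1 expects about 78 randomised subjects and 30% dropout, with no split by arm.

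**The concern.** The endpoint is a proportion: continent or not. A test on three categories by arm has 2 degrees of freedom and asks whether the whole distribution differs, missing included. It can reject because one arm lost more subjects, even when the share continent is the same in both. The p-value would nevertheless be reported under a continence heading.

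Unequal loss is plausible in this design. The active arm is titrated, a subject who cannot tolerate the reduced dose level is discontinued, and tolerability is the primary question. The effect does not depend on which arm loses more. A p-value of 0.05 or less would be declared significant, with no multiplicity adjustment among the efficacy endpoints.

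**Working it through.** **Inputs.** "Subjects will be randomly assigned to receive litoxetine or matched placebo BID in a 2:1 ratio" (SAP 3.2), so 78 subjects split as 78 × 2/3 = 52 litoxetine and 26 placebo. Overall missing is 30% (SAP 3.1). Alpha, rounding and the Fisher switch are as in SAP 6.3 and 6.9. The documents state no error rate or power for the continence test, so there is no figure of the plan's to reproduce here. Assumed, because the documents do not give them: continence of 10%, 20% or 30%, and the split of missing data by arm. Each split keeps 30% overall, for example (2 × 40% + 10%)/3 = 30%.

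**Worked table 1: equal continence among all randomised.**

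| | Litoxetine (52) | Placebo (26) | Expected |
|---|---|---|---|
| Continent | 10 (19.2%) | 5 (19.2%) | 10 / 5 |
| Not continent | 22 | 18 | 26.67 / 13.33 |
| Missing | 20 | 3 | 15.33 / 7.67 |

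Missing overall is 23/78 = 29.5%. One of six cells is below 5 (16.7%, not above 20%), so the SAP's rule selects chi-square. With X² = Σ(O − E)²/E:

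X² = 0 + 0 + 0.817 + 1.633 + 1.420 + 2.841 = 6.711. On 2 df, p = exp(−6.711/2) = 0.035, which is significant.

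The 2x2 test on the same data (10/52 versus 5/26, missing counted as not continent) gives p = 1.00.

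**Worked table 2: equal continence among observed subjects.** Continent 8 versus 6, not continent 24 versus 18 (8/32 and 6/24, 25% each), missing 20 versus 2. Here X² = 0.190 + 0.381 + 0.571 + 1.143 + 1.939 + 3.879 = 8.10, and p = exp(−8.10/2) = 0.017. The observed-case 2x2 gives p = 1.00.

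**Simulation.** There were 4,000 trials per scenario. The test was Pearson chi-square without continuity correction, replaced by the exact Fisher–Freeman–Halton test when more than 20% of cells had counts below 5. Rejection was rounded p ≤ 0.05. The Monte Carlo standard error is at most √(0.25/4000) = 0.8 percentage points. Rejection rate of the three-category test:

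| Continence, equal in both arms | 30 v 30% missing | 35 v 20% | 37.5 v 15% | 40 v 10% |
|---|---|---|---|---|
| 10% of all randomised | 4% | 23% | 49% | 79% |
| 20% of all randomised | 5% | 22% | 49% | 79% |
| 30% of all randomised | 6% | 25% | 54% | 83% |
| 10% of observed | 4% | 23% | 47% | 78% |
| 20% of observed | 5% | 21% | 46% | 75% |
| 30% of observed | 5% | 21% | 44% | 74% |

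The first column shows that the test holds its level when missingness is equal. The rise across columns comes from unequal missingness.

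**The alternatives at 40% versus 10% missing**, under the same switch rule, with continence of 10%, 20% and 30% in turn:

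| | Equal among all randomised | Equal among observed |
|---|---|---|
| 2x2, missing = not continent | 3%, 4%, 5% | 6%, 11%, 17% |
| 2x2, observed cases | 5%, 11%, 24% | 2%, 3%, 4% |

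If Fisher's exact test is used in every trial, the 17% becomes about 12%. Neither 2x2 is neutral under both definitions of equal continence, but both stay far below the three-category test.

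**The case against.** The strongest reply is that the SAP never draws the table. Continence is a yes/no state, the sentence on Missing follows the sentences on frequencies and denominator, and the test comes in a separate paragraph. Missing could be a display row beside a 2x2 test, and the all-at-baseline denominator fits that. This reading is possible, so it would go too far to say that the plan certainly tests three categories. But the SAP says Missing is part of the analysis, goes straight to a test whose form depends on the cells of a table, and nowhere names a 2x2.

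A second reply is that imputation leaves no missing values in the ITT population. If 6.1 and 6.3 cover continence, the Missing category in 6.9 is empty and the inflation cannot arise. The SAP points both ways. Continence is computed from the imputed count, yet 6.9 provides for Missing, and the no-imputation sensitivity analyses in 6.9.1 do not list continence. This is a conflict to resolve, not a defence of the text.

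A third reply is that chi-square would often not be the test used. At 10% continence of all randomised, the switch to Fisher's test is triggered in about 57%, 73% and 87% of trials across the three unequal splits. The simulated rates already apply the switch, so this does not reduce them.

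It also stands that the endpoint is secondary and exploratory in a trial whose primary aim is safety, and that a reader who sees the Missing row could suspect dropout as the cause.

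**Conclusion.** The point holds for the ITT continence test on the plain reading of SAP 6.9 point 3. With equal continence, rejection rises from about 4–6% at equal missingness to roughly 20–25%, 44–54% and 74–83% at the three unequal splits. These sizes rest on assumed splits and continence rates, and on 52 and 26 subjects. The ITT population could be slightly smaller, since it requires a dose and a valid baseline diary value.

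Three stronger conclusions might be inferred, and the documents do not support them:

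- That litoxetine will have more dropout, so a false continence finding is to be expected. The documents give no split by arm and describe the safety profile as acceptable. The inflation is conditional on unequal missingness.
- That every continence analysis is affected. PP subjects must have a Visit 6 value, so Missing is empty there.
- That counting missing as not continent removes the sensitivity to dropout. It does not if continence is equal only among observed subjects. At 30% continence and 40% versus 10% missing, the proportions on that definition are 0.30 × 0.60 = 18% and 0.30 × 0.90 = 27%, a difference due to dropout alone.

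The change should be made, but it does not touch the primary safety analysis.

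**What to change.** Amend SAP 6.9 point 3, before unblinding, to state that:

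1. The ITT test is 2x2, continent versus not continent, on all ITT subjects at baseline, with missing counted as not continent. This matches the denominator already specified.
2. Missing is shown as a descriptive row by arm and is not a category of the tested table.
3. The imputation in 6.1 and 6.3 does not apply to this endpoint. If the sponsor intends that it should, 6.9 must drop the Missing category and say how continence is derived and combined across imputations.
4. An observed-case 2x2 is reported as a sensitivity analysis, since the two rules respond to unequal dropout under opposite assumptions.

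The cost is a few SAP sentences and one extra output. No new data are needed. The downside to record is the remaining sensitivity of the main 2x2 at 40% versus 10% missing with continence equal among observed subjects: about 11% rejection at 20% continence, and about 12% (Fisher throughout) to 17% (the SAP's switch) at 30%. The three-category test rejects in about 75% in the same settings.

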8.8 Efficacy Endpoints and Analyses

8.8.1 *Efficacy Endpoints*

Baseline for all efficacy endpoints will be defined as the last week of the Screening Placebo Run-In Period.

- Percentage change from the end of the Screening Placebo Run-In Period to Week 8 in the number of incontinence episodes/24 hours
- Absolute change from the end of the Screening Placebo Run-In Period to Week 8 in the number of incontinence episodes/24 hours

Number of incontinence episodes/24 hours will be computed as Total Number of incontinence episodes recorded over the 7 days/7.

- Proportion of subjects who become continent at Week 8
- Change from end of the Screening Placebo Run-In Period to Week 8 in the number of incontinence pads used per week

8.8.2 *Efficacy Analyses*

The efficacy analysis will be performed on the ITT, mITT, and PP populations. The efficacy analysis will be performed on the ITT population, with the analysis on the mITT and PP populations as part of secondary efficacy analysis.

The efficacy analysis planned is a mixed effects model with repeated measures (MMRM). Percent reduction in incontinence episodes as the response variable is the first efficacy endpoint. The factor variable will be dose and the covariate will be baseline episodes (end of placebo run

in) of incontinence. Visits within subjects will provide the random effects of the mixed model. There is only one hypothesis so there will be no adjustment for multiplicity. Further efficacy analysis will be conducted similarly, with appropriate baseline measure. There will not be an adjustment for multiple comparisons for these secondary analyses.

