6.2 Covariate and Subgroups

Safety

Age (under 65, over 65) is used as subgroup for the analysis of treatment emergent adverse event.

Efficacy

The methodology described in the protocol for the efficacy analyses is a mixed model with repeated measures (MMRM). In light of the fact that the efficacy measurements were recorded at visit 2 and visit 6 only, there are no repeated measures. Therefore, the MMRM model described in the protocol cannot be applied to these analyses. The efficacy analyses will be conducted as an analysis of covariance (ANCOVA).

The model will include Baseline values as a covariate and dose and site as factor variables.

Baseline is defined as end of Screening Placebo Run-in for all efficacy analyses (Visit 2).

Exploratory efficacy analysis will be performed based on the baseline severity of incontinence episodes, as defined in section 5.4.2. Patients will be divided in 2 groups according to the median number of incontinence episodes.

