6.9 Efficacy Analyses

Efficacy will be assessed by the number of urinary incontinence episodes. There is only one hypothesis so there will be no adjustment for multiplicity.

The efficacy analysis will be performed on the ITT and PP populations.

There will not be an adjustment for multiple comparisons for these efficacy analyses.

Baseline for all efficacy endpoints will be defined as the last week of the Screening Placebo Run-In Period (Visit 2). The final measurement (endpoint) will be defined as Week 8 (Visit 6).

1. Percentage change from end of the Screening Placebo Run-In Period to Week 8 in the number of incontinence episodes in a week

The efficacy analysis planned is an analysis of covariance model (ANCOVA). Percentage change in the number incontinence episodes/week is the response variable. The factor variables will be dose and centre. If the center effect is significant, summary statistics will be presented to describe the effect. The covariate will be end of the Screening Placebo Run-In Period episodes of incontinence.

The percentage change, $\%UIE_i$, for subjects in each arm, is expressed as the ratio of the total number of urinary incontinence episodes in a week between final measurement ($UIE_{i,end}$) and baseline ($UIE_{i,base}$)

$$\%UIE_i = \frac{UIE_{i,end}}{UIE_{i,base}}$$

Since percentage change from baseline does not have the properties of additivity and symmetry, it will be log-transformed, and the response variable will be the natural logarithm of the ratio of Week 8 (Visit 6) to Baseline, as shown below:

$$\log(\%UIE_i) = \log\left(\frac{UIE_{i,end}}{UIE_{i,base}}\right)$$

The hypothesis test being conducted is as follows:

$$\begin{aligned} H_0: \log(\%UIE_{\text{Litoxetine}}) - \log(\%UIE_{\text{Placebo}}) &= 0 \\ H_1: \log(\%UIE_{\text{Litoxetine}}) - \log(\%UIE_{\text{Placebo}}) &\neq 0, \end{aligned}$$

This is equivalent to testing the hypothesis:

$$H_0: \log\left(\frac{\%UIE_{Litoxetine}}{\%UIE_{Placebo}}\right) = 0$$

The result of the ANCOVA model will be expressed as log % and then back transformed to percentage change. Therefore, H_0 can be interpreted as:

$$H_0: \frac{\%UIE_{Litoxetine}}{\%UIE_{Placebo}} = 1$$

This makes the actual statistics:

$$\delta = \log(\%UIE_{Litoxetine}) - \log(\%UIE_{Placebo}) = \log\left(\frac{\%UIE_{Litoxetine}}{\%UIE_{Placebo}}\right)$$

When back-transformed, this is expressed as follows:

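### The Week 8 continence comparison leaves out the baseline episode count; the planned test is valid, but adjusting for baseline would add a little power at almost no cost

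*SAP*

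**What the plan says.** - **SAP 6.9, point 3.** A subject is continent if there are no episodes at Visit 6. "Frequencies will be used to describe the proportion of subjects who are continent at Week 8". The denominator is every subject in the arm at baseline, and "The category Missing will be included in the analysis". The arms are compared as follows: "Differences between groups will be evaluated using Chi-square test or Fisher's exact test (if more than 20% of the cells" in the table have counts below 5). No covariate is named.
- **SAP 6.9, other points.** For percentage change and absolute change in episodes (points 1 and 2): "The covariate will be end of the Screening Placebo Run-In Period episodes of incontinence". Point 5 (nocturia) uses the same covariate. Point 4 adjusts for baseline pads.
- **SAP 6.2.** "The model will include Baseline values as a covariate and dose and site as factor variables". This follows directly on the statement that efficacy will be analysed by ANCOVA.
- **Protocol 8.8.2.** "Further efficacy analysis will be conducted similarly, with appropriate baseline measure".
- **Elsewhere.** No adjusted or stratified analysis of continence appears in SAP 6.9.1 or 6.9.2. The list of clarifications in SAP 1.5 does not mention that continence is analysed without baseline.

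**The concern.** Inclusion criterion 4 asks for at least 7 episodes a week and sets no upper limit. A subject who enters with 7 a week has less far to go to reach zero than one who enters with several times that number, yet the planned test treats them as equally likely to become dry. The randomisation text (protocol 4.4, SAP 3.2) names no stratification factor, so baseline severity is balanced only on average.

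What is at stake is efficiency: a predictor that is already measured is not used, and a chance imbalance in it is not corrected. The SAP's ITT definition (4.1) requires a valid baseline count, so the covariate is available for everyone in that population.

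**Working it through.** **The plan's own figure.** No continence rate or power is stated. The only sample-size figure is the ±14% half-width for a 50% safety event rate. With 78 × 2/3 = 52 on litoxetine, 1.96 × √(0.25/52) = 13.6%, so it reproduces. It says nothing about continence.

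**Inputs from the documents.** Allocation 2:1; 78 randomised (52 vs 26); 60 evaluable as stated (40 vs 20); two-sided alpha 0.05.

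**Assumed inputs.** Continence of 10% vs 30% or 20% vs 40% (placebo vs litoxetine), and an odds ratio (OR) of 1.5, 2 or 3 by which the odds of becoming dry fall per SD of log baseline count.

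**Power.** 6,000 simulated trials per row. The planned rule is read here as a 2×2 table with observed counts; the adjusted test is the logistic score test for arm.

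| Arms | Rates | OR per SD | Planned rule | Plain chi-square | Adjusted | Adjusted minus chi-square |
|---|---|---|---|---|---|---|
| 40/20 | 10 vs 30% | 1.5 | 36.3 | 40.4 | 41.6 | 1.2 |
| 40/20 | 10 vs 30% | 2 | 36.5 | 40.6 | 44.8 | 4.2 |
| 40/20 | 10 vs 30% | 3 | 37.8 | 41.8 | 48.2 | 6.4 |
| 40/20 | 20 vs 40% | 1.5 | 29.5 | 35.6 | 35.7 | 0.1 |
| 40/20 | 20 vs 40% | 2 | 29.4 | 35.7 | 37.6 | 1.9 |
| 40/20 | 20 vs 40% | 3 | 28.5 | 34.3 | 39.9 | 5.6 |
| 52/26 | 10 vs 30% | 1.5 | 46.6 | 53.7 | 53.8 | 0.1 |
| 52/26 | 10 vs 30% | 2 | 46.1 | 52.8 | 55.8 | 3.0 |
| 52/26 | 10 vs 30% | 3 | 46.4 | 53.3 | 59.4 | 6.1 |
| 52/26 | 20 vs 40% | 1.5 | 42.0 | 42.9 | 44.0 | 1.1 |
| 52/26 | 20 vs 40% | 2 | 42.6 | 43.6 | 46.4 | 2.8 |
| 52/26 | 20 vs 40% | 3 | 42.9 | 43.8 | 51.0 | 7.2 |

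The last column is the gain from using baseline: 0 to 1 point at OR 1.5, 2 to 4 at OR 2, and 6 to 7 at OR 3. It is nil if baseline is not prognostic.

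**How strong might baseline be?** If Week 8 counts were negative binomial with mean proportional to baseline, an assumed baseline median near 18 a week and dispersion k from 0.5 to 2, the implied OR per SD is about 1.35 to 2.35. That corresponds to a gain of roughly 0 to 5 points.

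**The Fisher part.** Plain chi-square minus planned rule is 4 to 7 points in three of the four blocks and about 1 point at 52/26 with 20% vs 40%. Other assumed rates took it to about 8. It exists only when the rule picks Fisher's test:
- In a 2×2 table one small cell is 1/4 = 25%, above the 20% trigger. With Missing as a third category it is 1/6 = 17%, below the trigger.
- At 52/26 with 10% vs 35%, Fisher's test is selected in 89% of 2×2 tables on observed counts, but in only 7–24% of 2×3 tables (missingness of 23–30% assumed).
- On expected counts the smallest cell is one third of all dry subjects, so it falls below 5 only with 14 or fewer dry in total. The expected total is 0.10 × 26 + 0.35 × 52 = 20.8, and Fisher's test is selected in about 4% of tables.
- Even on observed 2×2 counts, at 20% vs 40% it is selected in 38%.

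**Type I error** (10% dry in both arms): planned rule 2.9–3.2%, plain chi-square 4.1–4.7%, adjusted score test 4.5–5.8%. A likelihood-ratio test ran at 6–9%, which is why the score test is preferred.

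**Chance imbalance.** The SE of the baseline difference is √(1/52 + 1/26) = 0.24 SD, so 1 trial in 20 exceeds 1.96 × 0.24 = 0.47 SD. At OR 2 per SD, that shifts the odds ratio by 2^0.47 ≈ 1.4.

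**The case against.** The strongest reply is that nothing in the plan is in error. An unadjusted comparison is valid under randomisation, and chance imbalance in baseline is already covered by its type I error. Protocol and SAP describe efficacy as explored, the sample size rests on safety precision, and no power is claimed for continence. SAP 6.2 speaks of an ANCOVA model, which does not fit a yes/no outcome, and point 3 names its own test. The same diary counts are analysed with baseline adjustment in points 1 and 2. All of this stands. It limits the weight of the point but gives no reason to leave baseline out.

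Two further replies also stand. Part of the gain reflects a slightly looser test, since the adjusted test runs nearer to, and at times just above, 5%. And a binary model is incomplete until the plan says what happens to missing Visit 6 values, a choice that could matter more than the covariate.

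A reader might infer that the rule will usually fall to Fisher's test and that this loss belongs to the missing covariate. The documents do not support that. Point 3 keeps a Missing category and does not say whether counts are observed or expected, and Fisher's conservatism is a separate matter from baseline.

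**Conclusion.** The point holds as a small efficiency and consistency improvement. Leaving out baseline costs roughly 0 to 5 points of power at moderate prognostic strength (OR per SD up to about 2.35) and about 7 at OR 3. A further 4 to 8 points are in play only under the 2×2, observed-count reading. Power stays low with either method: about 29–59% for a 20-point difference in the table above.

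All of this rests on assumed continence rates, baseline spread and slope. Site effects and the Missing category were not modelled.

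Two stronger readings should be resisted. One is that the planned test is biased or invalid; it is not. The other is that adjustment would bring gains above 10 points. Against plain chi-square these appeared (11 to 15 points) only at an assumed OR of 5 per SD, well beyond the range that the count model suggests, and nothing in the documents indicates such strength.

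Severity: nice to have.

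**What to change.** Amend SAP 6.9, point 3, before unblinding:

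- Make the arm comparison a logistic regression of continence (yes/no) on randomised arm and log baseline weekly episodes, with a score test for arm. Include no site term: up to 15 sites cannot be supported by the roughly 14 to 26 continent subjects expected in the scenarios above (from 0.10 × 20 + 0.30 × 40 = 14 to 0.20 × 26 + 0.40 × 52 = 26).
- Count subjects with a missing Visit 6 value as not continent, in line with the stated denominator of all subjects at baseline. Give an observed-cases version as sensitivity.
- Report the adjusted odds ratio with a 95% CI by one prespecified small-sample method, for example Firth penalised likelihood in all cases, not only when an arm has no events. State that the score test supplies the p-value, since the two can differ near the margin.
- Keep the crude proportions, the Missing count and the planned chi-square or Fisher p-value as supporting output, and say whether that table is 2×2 or 2×3 and whether the 20% rule uses observed or expected counts.

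The cost is a few lines of SAP text and one model; the SAP already plans logistic regression for adverse events (6.8). The small downside is that the odds ratio is conditional on baseline, so the crude proportions should stand beside it.

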5.4 Efficacy Variables

Bladder Diary Questions

The bladder diary will be completed daily for the 7 days prior to visit 2 and visit 6, to record the number of incontinence episodes and whether these were nocturia events. If a subject has multiple events in 1 day, each event will preferably be entered separately. The number of incontinence pads used will also be recorded in the diary.

Percentage change in number of incontinence episodes in a week

The number of incontinence episodes entered into the eCRF is the total number of events a subject recorded during the 7day period prior to visit 2 and visit 6. This number will be directly used in the calculation of % change in number of incontinence episodes in a week

Number of Incontinence Episodes/24 hours (daily average)

The number of incontinence episodes entered in the eCRF will be divided by 7 to compute the number of episodes/24 hours (daily average). This consideration follows the assumption that the bladder diary will be filled by the subject for the 7 days prior to Visit 2 and Visit 6 and that the patient entered all episodes occurred in this period. Therefore, the following formula will be used:

$$\text{Number of Incontinence episodes / 24 hours} = \frac{\text{Number of incontinence episodes recorded}}{7}$$

Number of Nocturia Episodes in a week

The number of nocturia episodes entered in the eCRF is the total number of nocturia episodes a subject recorded during the 7day period prior to Visit 2 and Visit 6. The value entered in the eCRF will be used in the efficacy analysis of nocturia episodes without any adjustment.

Number of Incontinence Pads per week

The number of incontinence pads entered in the diary represents the number of pads used in a week, therefore the value entered in the eCRF will be used in the analysis without any adjustment.

This consideration follows the assumption that the bladder diary is completed by the subject for the 7 days prior to Visit 2 and Visit 6 and that the patient entered all pads used in this period.

Proportion of subjects who become continent

A subject is defined as continent if he/she has no incontinence episodes.

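### The nocturia ANCOVA (SAP 6.9 point 5) adjusts for baseline incontinence episodes instead of baseline nocturia

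*SAP*

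**What the plan says.** Nocturia is the fifth secondary endpoint in SAP 2.4. SAP 1.5 item a says that it was added in the SAP. For this endpoint SAP 6.9 point 5 states: "Percentage change in the total number of nocturia episodes in a week is the response variable". The factors are dose and centre, and then: "The covariate will be end of the Screening Placebo Run-In Period episodes of incontinence". Point 5 ends by referring back: "The analysis will be carried out as described in section 6.9 point 1". Point 1 takes the log of the Visit 6 to baseline ratio as its response.

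Three other places bear on the choice of covariate:
- SAP 6.9 point 4, on pads: "The covariate will be the number of pads used at the end of the Screening Placebo Run-In Period".
- SAP 6.2, for the efficacy ANCOVAs in general: "The model will include Baseline values as a covariate and dose and site as factor variables".
- Protocol 8.8.2: "Further efficacy analysis will be conducted similarly, with appropriate baseline measure".

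Under SAP 5.4, nocturia is entered in the eCRF as its own weekly count for the 7 days before Visit 2 and before Visit 6. SAP 6.1 excludes nocturia from the multiple imputation.

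**The concern.** In an ANCOVA of change, the endpoint's own baseline is normally the strongest predictor of the change, partly through regression to the mean. A patient whose run-in week happened to contain many nocturia episodes will tend to show a fall whatever the treatment. Total incontinence carries only part of that information. Adjusting for it instead costs some precision and leaves a chance difference between arms in baseline nocturia mostly uncorrected.

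No reason is given for the choice. The wording matches points 1 and 2, so it looks like a sentence carried over without change. The closing reference to point 1 does not repair it, because point 1 names the same covariate.

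**Working it through.** **Text check.** The endpoints of SAP 6.9 side by side:

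| Point | Response | Baseline covariate |
|---|---|---|
| 1 | log ratio, weekly incontinence | incontinence |
| 2 | absolute change, incontinence per 24 h | incontinence |
| 3 | proportion continent | none (chi-square or Fisher) |
| 4 | absolute change, weekly pads | pads |
| 5 | log ratio, weekly nocturia | incontinence |

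Of the four ANCOVA endpoints, only point 5 lacks its own baseline. The plan states no power or effect size for nocturia, so there is no figure to reproduce.

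**Size of the effect: inputs.** From the documents: 60 evaluable patients (SAP 3.1), split 2:1, so 60 × 2/3 = 40 on litoxetine and 20 on placebo; at least 7 incontinence episodes a week at entry (Protocol 4.1); log-ratio response (SAP 6.9). A 30% dropout from 78 would leave 78 × 0.7 ≈ 55. That affects the standard errors more than the comparison between covariates.

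Assumed, because the documents give no nocturia distribution:
- Weekly incontinence rate: gamma, shape 2, mean 20.
- Nocturnal share: beta, mean 0.1, 0.2 or 0.4, concentration 2 or 5.
- Night and day counts: Poisson, so nocturia is a subset of incontinence, as the diary description suggests.
- Individual change to Week 8: lognormal, SD 0.3 or 0.8.
- True litoxetine/placebo ratio 0.5; zeros replaced by 0.4; no site factor.

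This gives 3 × 2 × 2 = 12 settings, each simulated repeatedly with different seeds. The ranges below cover settings and runs.

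| Covariate | Variance cut against SAP covariate | Factor on the ratio if mean log baseline nocturia is 1 SD higher on litoxetine |
|---|---|---|
| Incontinence count (SAP) | reference | 0.91 to 0.96 |
| Nocturia count | 0% to 8% | 0.96 to 0.99 |
| Log nocturia count | 4% to 17% | 1.00 to 1.03 |

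One SD of chance imbalance is 0.27 to 0.38 log units. In patient numbers, an 8% cut is worth 60/0.92 ≈ 65 patients instead of 60, and a 17% cut 60/0.83 ≈ 72. The estimate has a standard error of about 0.19 to 0.29 log units, and ln(0.91) ≈ −0.09. So a 1-SD imbalance moves the result by at most about half a standard error (0.09/0.19 ≈ 0.5).

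**Cross-check with a simpler model.** Let ρ be the correlation of baseline and Week 8 log nocturia, and r that of baseline nocturia and baseline incontinence. Assume equal variances, and that incontinence acts only through baseline nocturia. The variance ratio, SAP covariate over own baseline, is then 1 + (1−ρ)(1−r²)/(1+ρ).
- ρ = 0.7, r = 0.6: 1 + 0.3 × 0.64/1.7 = 1.11, a cut of 1 − 1/1.11 ≈ 10%.
- ρ = 0.3, r = 0.1: 1 + 0.7 × 0.99/1.3 = 1.53, a cut of 1 − 1/1.53 ≈ 35%.

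This model works on the log scale, so its 10% to 35% compares with the 4% to 17% above. The direction is the same; the size depends on the assumptions.

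**Zero baselines.** In the same simulation 3% to 59% of patients have no nocturia at baseline. With 0.4 at both visits, a patient going from 0 to 0 scores no change and cannot improve, and one going from 0 to 1 scores 1/0.4 − 1 = +150%. The true ratio of 0.5 is then estimated at about 0.49 to 0.76, whichever covariate is used. Leaving out zero-baseline patients while keeping 0.4 at Visit 6 gives about 0.49 to 0.57, with larger variance in most settings.

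**The case against.** The best defence is that the slip hardly matters. Nocturia events are flagged among the incontinence episodes, so total incontinence is a partial proxy. The endpoint is fifth among the secondaries and was added in the SAP of a trial whose primary objective is safety. Correcting the covariate alone gains at most about 8% in variance. All of this stands, and it limits the weight of the point. It does not explain why point 5 should differ from point 4.

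It is also fair to say that a log-scale covariate goes beyond correcting a slip. Points 1, 2 and 4 use plain counts, so logging only point 5 would be a refinement and is not needed for consistency.

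Two stronger readings are tempting. A reader might infer that the nocturia comparison is biased. It is not: under randomisation either covariate is legitimate, and the mean estimates agreed within 0.006 on the log scale.

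A reader might also infer that nocturia zeros will be dropped, because the zero rule names incontinence only ("Numbers of incontinence episodes equal to 0 (not missing) will be imputed as 0.4 to allow for the log transformation") and SAP 5.4 says of nocturia: "The value entered in the eCRF will be used in the efficacy analysis of nocturia episodes without any adjustment". The documents do not support this. Point 5 adopts the method of point 1, so carrying 0.4 over is the natural reading. SAP 5.4 uses the same no-adjustment wording for pads, in contrast to dividing by 7 for the daily average, and this does not conflict with the 0.4 rule.

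**Conclusion.** The covariate in SAP 6.9 point 5 is the wrong baseline for its endpoint and departs from SAP 6.2, Protocol 8.8.2 and the plan's own treatment of pads. This rests on the text and needs no assumptions. The consequence is a small loss of precision and weaker control of chance imbalance, not bias. The percentages depend on assumed distributions and should be read as orders of magnitude.

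A secondary gap remains. Point 1's zero rule was written for an endpoint whose baseline cannot be zero in eligible patients, and nocturia has no such floor. Using 0.4 at both visits keeps every patient but attenuates the effect when zero baselines are common; leaving those patients out reduces the attenuation but usually costs precision. That is a trade-off for the sponsor to settle.

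**What to change.** In SAP 6.9 point 5, replace the covariate sentence so that it names the weekly number of nocturia episodes from the last week of the run-in (Visit 2). Taking that covariate on the log scale, to match the log-ratio response, is optional and gains more precision; with the log scale, state how zeros enter the covariate as well.

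In the same place, state before unblinding how patients with zero baseline nocturia are handled in the log ratio.

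The cost is one term in the program and two sentences in the SAP. The data are already in the eCRF, and correcting the covariate removes no patient.
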